All AEs / SAEs related to the intervention or trial protocols that occur between baseline and the end of an individual's participation in the study will be recorded in their participation notes, in the appropriate section of the trial CRF, and the study AE / SAE log kept by the chief investigator, site leads, and trial manager. Any contacts completed as part of the intervention will be recorded in participant's medical notes, including a summary of any AE / SAE.

Research and clinical trial staff will be required to report any SAEs immediately and within 24 hours of becoming aware of the event using a set reporting template. The chair (or in their absence, deputy chair) of the TSC will independently review all SAE. The chair will discuss any RSAR / RUSAE with the wider TSC who can then recommend pausing the research while an investigation is completed and learning implemented, or stopping it completely. The chief investigator will notify the REC and funder of any RSAR / RUSAE as soon as possible, but within 15 days of becoming aware of these as per HRA guidance.

The chief investigator will also review all SAE to assess whether they are likely to be the result of any aspect of the trial procedures or intervention (i.e. RSAR / RUSAE). In cases of immediate and obvious concerns about participants' health or safety, the chief investigator may employ urgent safety measures and immediately stop the trial, notifying the research ethics committee (REC) of this decision immediately over the telephone and within three days in writing (as per HRA guidelines).

Given the target sample of people with SMI, we expect there to be some SAEs relating to lifethreatening behaviour (i.e. suicide attempts) across both arms of the project. The TSC, trial management team, and Sponsor will monitor and review the number of SAE in the two arms of the trial. Should we record considerably higher rates of SAE in either arm, the TSC will convene and may recommend pausing the research whilst investigating further or stopping it completely. Due to the increased number of planned participant contacts in the intervention arm (n=6), compared to the TAU arm, we may identify a greater number of SAE through increased monitoring in the treatment arm. Therefore, an unequal distribution of SAE will not automatically act as stopping criteria, but would be carefully monitored, reviewed, and actioned as appropriate.

23. Auditing

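### On its plain reading, Protocol section 22 sends only related SAEs to the CRF and log, while section 12 promises by-arm counts of all SAEs

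*Protocol*

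**What the plan says.** Protocol section 22 (Harms), under Reporting of adverse events, begins: "All AEs / SAEs related to the intervention or trial protocols that occur between baseline and the end of" each person's time in the trial. Such events "will be recorded in their participation notes, in the appropriate section of the trial CRF, and the study AE / SAE log". No other sentence in section 22 assigns events to the CRF or the log.

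The following paragraphs of the same section are wider:

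- Staff must "report any SAEs immediately and within 24 hours of becoming aware of the event using a set reporting template".
- The chair (or deputy) "of the TSC will independently review all SAE".
- "The chief investigator will also review all SAE to assess whether they are likely to be the result of any aspect", meaning link work or anything else done for the trial.
- On comparison by arm: "The TSC, trial management team, and Sponsor will monitor and review the number of SAE in the two arms of the trial".
- If rates prove markedly higher in one arm, the committee meets and can advise a pause for investigation or a complete stop.

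Section 12 (Outcomes), in the paragraph on SAEs after Table 1, undertakes to record and report for each arm how many SAEs occur and how many participants have one or more. It sets no relatedness condition. It then names adverse reactions and serious adverse reactions as a separate, causally attributed group.

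**The concern.** The record described first in section 22 is narrower than the outcome promised in section 12 and the monitoring described later in section 22. A site that follows the opening sentence could properly leave an unrelated SAE off the CRF and log, although it would still send the 24-hour report.

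Such events are foreseen. In section 22 the team writes that "we expect there to be some SAEs relating to lifethreatening behaviour (i.e. suicide attempts) across both arms of the project", and the definitions table says that SAEs are expected because of the population. Many of these may have nothing to do with link work or the assessments.

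At stake is a by-arm safety count that will be published and passed to those planning a definitive trial; section 7 lists safety among the key outputs. If the count is taken from a record filtered on relatedness, it would be labelled as SAEs but would contain only a subset. That subset would also be selected differently in the two arms.

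**Working it through.** The documents give no SAE rate and no related share, so there is nothing to recompute. The check sets the scope of each provision side by side.

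| Provision | Where | Events covered |
|---|---|---|
| Entry in notes, CRF and AE/SAE log | Section 22, first sentence under Reporting | Related to the intervention or trial protocols |
| 24-hour report on a template | Section 22, second paragraph | Any SAE |
| Review by TSC chair | Section 22, second paragraph | All SAEs |
| Review by chief investigator, including relatedness | Section 22, third paragraph | All SAEs |
| Monitoring of numbers by arm | Section 22, last paragraph | SAEs, no relatedness limit |
| Recording and reporting by arm | Section 12, SAE paragraph | SAEs, no relatedness limit |
| Definition of an AE | Section 22, definitions table | Related or not, untreated controls included |

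1. **Scope.** The first row is the only one restricted to related events. Section 12 handles causally attributed reactions separately from SAEs, so its SAE counts are meant to be all-cause. The two scopes do not match.

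2. **Order.** Relatedness is assessed at the chief investigator's review of all SAEs. A record that admits only related events applies the filter before that review.

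3. **Whether another route fills the gap.** The 24-hour template captures every SAE in both arms, so the information exists. The protocol does not say that template reports are transcribed to the CRF or log. Section 22 also has intervention contacts written up in the medical notes with a summary of any AE or SAE, but that route exists only where there are intervention contacts. It does not serve the treatment-as-usual (TAU) arm.

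4. **Comparability.** A participant in the link-work arm can have an event related to link work or to trial procedures. A TAU participant receives no link work, so an event there could qualify only through trial procedures. A related-only count therefore applies different entry conditions in the two arms.

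5. **Likely source of the counts.** Section 19 (Data management) places the main database at the clinical trials centre. Section 32 (Trial management) gives that centre responsibility for the eCRF and has its statistical research assistant do the final analysis. Drawing the SAE table from the CRF is thus a realistic route, but neither section says so.

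6. **The SAP.** The SAP supplied was written for a different trial (a student suicidality trial of an imagery intervention), so it does not settle which source is used here.

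**The case against.** The strongest reply is that the opening sentence excludes nothing. It says that related events will be recorded, without the word *only*, and can be read as a minimum duty alongside the broader one in section 12. Every SAE must in any case be reported, reviewed by two people and monitored by arm. To publish a related-only count, someone would have to disregard section 12 and the 24-hour reports. The CRF is not among the documents, so its SAE page cannot be checked, and the log is kept by the chief investigator, site leads and trial manager. The definitions table also refers to the reporting investigator's opinion on causality, so some view at site may precede the central review.

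Much of this stands. It means that the restriction is the plain reading rather than an express exclusion, and that the route to a wrong count is inferred. It does not remove the mismatch: the one sentence that tells sites what to enter is narrower than the outcome to be reported, and no sentence links the complete source to the CRF or log.

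A reader might infer three stronger things that the documents do not support:

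- *That unrelated SAEs escape safety review.* They do not; the 24-hour reports go to review whatever their cause.
- *That the TSC's ability to pause or stop the trial is disabled.* The by-arm monitoring is worded for SAEs without restriction. The same paragraph also says that an imbalance does not by itself trigger stopping, and that the additional planned contacts in the link-work arm (n=6) may bring more SAEs to light there. All-SAE counts therefore carry a detection difference of their own, which better recording will not remove.
- *That feasibility criterion (vi) in section 12 must be changed too.* It speaks of research-related SAEs, but its decision rule is whether the intervention or procedures raise risk, and it adds TSC oversight of SAEs across arms. That can be read coherently, and widening it would change a stated success criterion.

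**Conclusion.** The point holds as an inconsistency in recording scope that is worth correcting. It is not a gap in safety oversight. By-arm SAE counts taken from the CRF or log as section 22 is worded could omit unrelated events and would not be like for like. Counts taken from the 24-hour reports would be complete.

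The conclusion rests on the plain reading of the opening sentence, and on the protocol's silence about whether the 24-hour reports feed the CRF and log. If the CRF already collects all SAEs, or the counts are drawn from the templates, nothing is lost. The size of any distortion cannot be estimated: it depends on the number of SAEs in each arm and the share judged related, and the documents give neither. Confidence is high on the mismatch in wording and lower on whether it would affect the published counts.

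**What to change.** Reconcile the passages by rewording the opening sentence under Reporting of adverse events in section 22, so that:

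- all SAEs in both arms, from baseline to the end of participation, are entered in the CRF and AE/SAE log regardless of relatedness;
- these entries are fed by the 24-hour reports already required;
- related and related-unexpected events (RSAR and RUSAE) are flagged as a subset after the existing reviews.

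State that this record is the source of the by-arm counts promised in section 12. The sentence also covers non-serious AEs; nothing here requires their scope to change, so the two should be worded separately. When the counts are reported, repeat the protocol's own caveat that more contact in the link-work arm may detect more SAEs.

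The cost is a minor protocol amendment submitted under section 25, more entries on the CRF and log, and possibly back-entry from existing reports for participants already enrolled. Back-entry may arise because the amendment table records a recruitment extension agreed in January 2023. No new SAE collection route is needed.

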- 2. To identify what training needs exist for support workers around link work.
- 3. To determine whether patients with SMI are willing to be randomised to a trial targeting dental visiting.
- 4. To understand whether it is feasible to collect clinical outcome and planned dental appointment data in this population.
- 5. To explore if, and how, patients with SMI engage with a link work intervention.
- 6. To understand the potential factors impacting (e.g. facilitators and barriers) acceptability and delivery.

Key outputs

1. A best practice manual to aid the link work intervention that is structured; easy to understand and implement; accounts for different service configurations; user-friendly for support workers; and helpful and acceptable to people with SMI.

- 2. Data on the acceptability and feasibility of assessing clinical and dental visiting outcomes.
- 3. Information on rates of recruitment, willingness to consent, adherence to treatment, attrition, missing data, and safety.
- 4. Data on outcomes and retention rates on which to base a sample size calculation for a definitive trial.
- 5. Qualitative data to configure and optimise the intervention and trial design.

8. Trial design

We will conduct a randomised controlled feasibility trial with two groups. Participants will be randomised at a ratio of 1:1 to either: Treatment as usual (TAU) or TAU plus the link work intervention. Both arms will also receive any concomitant interventions deemed necessary as part of their routine care. Research assistants (RAs) and a dental therapist will assess clinical outcomes, including self-report and objective oral health outcomes, self-esteem, self-efficacy, and depression at baseline and after nine months. Embedded qualitative work will explore trial and intervention processes.

9. Study settings

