- Pain related disability using the Manchester Orofacial Pain Disability Scale [62]
- Oral health related quality of life using the Oral Health Impact Profile [63].
- Self-efficacy around dental visiting will be measured using an item adapted from Armitage et al 64]: '*How confident are you that you will be able to attend a dental appointment*?' (1, no confident; 7, very confident).
- Self-esteem using the Rosenberg Self-esteem Scale (RSES; [65])
- Dental anxiety using the Modified Dental Anxiety Scale [66]

- Depression using the Patient Health Questionnaire [67]
- Quality adjusted life year using the EuroQol 5 Dimension (EQ-5D-5L [68])

At baseline, we will assess bruxism using items from Aggarwal et al [69]: 'Do you grind you teeth during the day or at night?' Yes/No. 'Has someone told you that you grind your teeth?' Yes/No and hyposalivation through the item 'Does your mouth usually feel dry?' Yes/No [X] for descriptive purposes. The Mini International Neuropsychiatric Interview [71](excluding suicidal behaviour, antisocial personality disorder or eating disorder subscales) will be included as a baseline measure to assess mental health diagnosis and understand the diagnostic composition of the sample.

Demographic and clinical information will include ethnicity, diagnosis, medication, illness length, inpatient admissions, service, cigarette/substance/alcohol use (items from [72]). We will assess attendance at urgent dental services, GP, A&E, or mental health wards, and prescription of antibiotics or painkillers. To assess the feasibility of assessing clinical information as secondary outcomes for a main trail, we will also collect data on whether the person has access to free dental care, is currently on a dentist list, the number of routine dental visits, and data on self-management, namely use of *brushing, flossing, and mouthwash*. We will record data on the number and length of intervention related activity (e.g. delivery, clinical note keeping, clinical supervision) to calculate estimates of the costs of the intervention.

Assessment	Baseline	Nine month follow-up
Demographic information	\checkmark	
Background clinical information	\checkmark	
Updated clinical information		\checkmark
Self-report dental visiting	\checkmark	\checkmark
BSA recorded dental visiting	\checkmark	\checkmark
Decayed, missing, or filled teeth (DMFT): Dental examination	✓	✓
Pulpal involvement, ulceration due to trauma, fistula, and abscess (PUFA): Dental examination	✓	✓

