Modified Plaque Score: Dental examination	\checkmark	\checkmark
Brief Pain Inventory (BPI)	\checkmark	\checkmark
Manchester Orofacial Pain Disability Scale (MOPDS)	\checkmark	✓
Oral Health Impact Profile (OHIP)	\checkmark	✓
Self-report bruxism / dry mouth	\checkmark	
Self-efficacy item	\checkmark	✓
Rosenberg Self-Esteem Scale (RSES)	\checkmark	✓
Modified Dental Anxiety Scale	\checkmark	✓
Patient Health Questionnaire -9	\checkmark	\checkmark
EQ-5D-5	\checkmark	✓
Mini International Neuropsychiatric Interview	\checkmark	

Table 1. Summary of assessment time points.

RAs will recruit participants, deliver self-report assessments, arrange appointments, complete paperwork and data entry, write field notes, and facilitate data extraction from notes. They will send out reminders and thank you messages to participants every three months to increase engagement with the trial protocols and reduce attrition.

We will record the number of serious adverse events and number of participants with at least one serious adverse event, and report these for the two study arms. We define a serious adverse event as any untoward medical occurrence that: results in death; is life threatening; requires inpatient hospitalisation or prolongation of existing hospitalisation; or results in persistent or significant disability/incapacity. Other important medical events may also be considered serious if they jeopardize the participant or require an intervention to prevent one of the above consequences. We will also measure adverse reactions and serious adverse reactions. The latter are adverse events that are both serious and, in the opinion of the reporting investigator, believed with reasonable probability to be due to the link work intervention, assessments, or qualitative interview, based on the information provided.

We will reimburse participants £20 for each of the assessments (baseline and nine-months) plus additional costs incurred for travel. This is based on INVOLVE guidance, PPI feedback, and is consistent with our past trials. Participants will be recognised and thanked for taking part in letters sent during the project and the dissemination materials, whilst maintaining confidentiality. There will be no payments for engaging with the intervention sessions.

Dental examination

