The target sample size is 84 participants (42 per group) with a recruitment rate of four participants per month for seven months at each of the three sites. The sample size has been calculated to ensure that for our feasibility proportions (from criteria i) to iii)), if we observe a proportion of 70% or more, that the lower end of the 95% confidence interval will be above the 60% amber/red cut-off. 28 per site will enable learning across locations and service provisions, increasing generalisability of the findings. We have an excellent record of recruiting and retaining patients with SMI from a variety of backgrounds in clinical trials [e.g. 76, 77].

15. Recruitment

We will recruit from secondary care services (EIS, CMHT) in three participating NHS Trusts, namely LSCFT, GMMH, and PCFT. Our definition of CMHTs includes community care hubs and any other new terms for community secondary care mental health services. It also includes any specialist service working into the CMHT (e.g. hub and spoke model psychological therapy teams, occupational therapy services). The research team have excellent working collaborations with these organisations with most holding joint appointments. Each site will have a designated research assistant (RA1-3) who will facilitate recruitment. Typically, this will involve meeting with clinical services (e.g. attending team meetings) to inform them about the study and share recruitment materials (e.g. information packs). Clinical staff will then disseminate the research to

participants who can opt into taking part with support from clinical studies officers (CSOs)/Assistant Clinical Research Practitioners (ACRPs) and the study research assistants.

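### A modest excess of SAEs in the link-work arm could not be told from extra detection, because the protocol describes no common SAE enquiry and no record of how each event was found

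*Protocol*

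**What the plan says.** Protocol Section 22 (Reporting of adverse events) notes that the intervention arm has more planned contacts than TAU, giving the number as six; Section 11 sets six as the maximum number of sessions. It then says that "we may identify a greater number of SAE through increased monitoring in the treatment arm" and that, for this reason, "an unequal distribution of SAE will not automatically act as stopping criteria". The sentence ends by promising that such an imbalance would be monitored, reviewed and acted on. Just before it, the section has the TSC convene, with power to recommend a pause or stop, if SAE rates are considerably higher in either arm. No number is attached.

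The by-arm comparison is planned. Section 12 reports the number of SAEs and the number of participants with at least one, for each arm, and makes safety feasibility criterion (vi).

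Other routes to an SAE exist in both arms:
- Section 12, on service use: "We will assess attendance at urgent dental services, GP, A&E, or mental health wards". That these items are repeated at nine months is inferred from the updated clinical information row of Table 1.
- Section 12 has research assistants "facilitate data extraction from notes".
- Section 18 has telephone check-ins.
- Section 22 has risk information from the referring clinician throughout the study.

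Section 22 also has intervention contacts written into the medical notes, with a summary of any AE or SAE. The supplied SAP describes a different trial (university students, an imagery intervention) and adds nothing on this point.

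**The concern.** The protocol identifies a detection bias and describes nothing that would reduce or measure it. Events found through routes common to both arms are pooled with events that only a support worker's contact could reveal. If the link-work arm shows somewhat more SAEs, the TSC will have to judge whether that is harm or closer observation, and the planned data do not let it separate the two.

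The recording rule may add a second asymmetry. One sentence in Section 22 limits recording to AEs and SAEs related to the intervention or trial protocols. Elsewhere Section 22 defines adverse events regardless of cause and includes untreated controls, and Sections 12 and 22 compare all SAEs by arm. Read literally, the narrower sentence could remove unrelated events, which are most of what TAU can contribute.

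A feasibility trial is the place to find out whether SAE ascertainment works, before a definitive trial inherits it.

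**Working it through.** **1. The plan's own figure.** Section 14 justifies 84 participants by feasibility proportions: "if we observe a proportion of 70% or more", then "the lower end of the 95% confidence interval will be above the 60% amber/red cut-off". By the Wald formula, 0.70 − 1.96 × √(0.70 × 0.30 / 84) = 0.602, so the statement reproduces. It holds with that formula only: the Wilson limit is 0.595 and the exact limit 0.590. The number also equals 4 per month × 7 months × 3 sites. Nothing in it concerns SAEs. The documents give no SAE rate, detection fraction or SAE threshold, so every rate and fraction below is an assumption.

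**2. Spurious ratio with equal true risk.** If a share d of affected participants is detected in each arm, observed ratio = true ratio × d(link work) / d(TAU). With 60-80% detected in TAU and 90-100% in link work:
- smallest: 0.90 / 0.80 = 1.13
- largest: 1.00 / 0.60 = 1.67

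At an assumed true risk of 20%, 42 × 0.20 = 8.4 participants per arm are affected. TAU would record 8.4 × 0.60 = 5.0 to 8.4 × 0.80 = 6.7, and link work 8.4 × 0.90 = 7.6 to 8.4.

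Read backwards, an observed ratio of 1.5 fits a true ratio anywhere from 1.5 / 1.67 = 0.90 to 1.5 / 1.125 = 1.33, before any sampling error.

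**3. How often an artefact would appear.** Equal true risk of 10% (assumed), 42 per arm, exact binomial enumeration:

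| Detection, link work v TAU | Ratio | Expected affected | More affected in link work | At least two-fold, with 3 or more affected |
|---|---|---|---|---|
| 90% v 90% | 1.00 | 3.8 v 3.8 | 42% | 20% |
| 100% v 90% | 1.11 | 4.2 v 3.8 | 49% | 24% |
| 100% v 75% | 1.33 | 4.2 v 3.2 | 58% | 33% |
| 100% v 50% | 2.00 | 4.2 v 2.1 | 75% | 52% |

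With 100% v 50% detection, the last column is 28%, 52%, 56% and 56% at true risks of 5%, 10%, 15% and 20%. With 90% in both arms it is 16%, 20%, 15% and 10%.

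**4. What would still stand out.** Fisher's exact test (two-sided p < 0.05, 42 per arm) needs 6 v 0, 8 v 1, 9 v 2 or 12 v 4. At 10% true risk, detection bias alone produces such a link-work excess in 1.3%, 2.1% and 4.8% of trials for the last three rows of the table. With 50% TAU detection it ranges from 0.6% to 17.5% across true risks of 5-20%.

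**5. What equal ascertainment would leave.** The spurious ratio becomes 1.0, but precision does not improve. The half-width is 1.96 × √(2p(1 − p) / 42).

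| TAU risk (assumed) | 95% half-width for difference | Fisher power for a true doubling | n per arm for 80% power (normal approximation) |
|---|---|---|---|
| 5% | 9.3 points | 4.8% | 435 |
| 10% | 12.8 points | 17.5% | 199 |
| 15% | 15.3 points | 30.0% | 121 |
| 20% | 17.1 points | 43.6% | 82 |

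**The case against.** The best reply is that the protocol does not rest its safety decision on the by-arm count. Criterion (vi) concerns research-related SAEs. The TSC chair independently reviews every SAE, the chief investigator assesses each for a link to the trial, and related events go to the wider TSC. None of this needs equal detection. SAEs here are deaths, admissions, A&E-level events and the like, in patients who are all under secondary mental health care, so many should reach the notes or the service-use items in either arm. TAU detection may therefore be well above 60%. The reporting template, CRF and monitoring plan are not supplied and could contain a source field.

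Most of this stands, and it rules out three stronger readings that a reader might infer:
- **That the protocol explains imbalance away.** It says only that an imbalance is not an automatic trigger. The sentence goes on to promise action, and the TSC convenes on considerably higher rates in either arm.
- **That the comparison can neither show nor exclude harm.** The bias runs towards excess in the link-work arm, so finding no excess would be conservative with respect to it. A large excess would be visible. The difficulty in excluding harm comes mainly from 42 per arm.
- **That the safety criterion carries no information.** The case-by-case causality review is informative whatever the detection rates.

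What the reply does not answer is the middle ground. A modest excess is the likeliest form an imbalance would take, and for that the supplied text offers no means of separating harm from detection.

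**Conclusion.** The point holds in a limited form. The protocol concedes unequal detection and compares SAEs by arm, yet describes neither a common enquiry nor a record of detection source. A modest link-work excess is therefore not interpretable. Under assumed detection of 60-80% v 90-100%, the artefact is a ratio of 1.13 to 1.67. That range depends on the assumed fractions, not on the SAE rate, and would shrink towards 1 if TAU detection were nearly complete. The enumerations further assume independent participants and one detection fraction per arm.

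The wording on which SAEs are recorded is a separate inconsistency and must be reconciled whatever the size of the bias. In a low-risk feasibility trial with descriptive reporting, this is a cheap improvement rather than a fault that undermines the safety oversight.

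**What to change.** - Keep the full by-arm table of all SAEs.
- On the SAE form, record every source through which each event was identified: nine-month service-use items, notes, check-in, referring clinician, intervention contact. Recording only who reported first is not enough. Support workers must report within 24 hours and will often be first with events that common sources would also reveal; sorting on first report would remove these from the link-work arm alone and reverse the bias.
- Apply the nine-month items and the planned notes extraction identically in both arms. Do not count support-worker entries in the notes as a common source, and time the notes check so that it does not unblind assessors.
- Add a second by-arm table of SAEs identifiable from sources common to both arms, whoever reported them first. List separately those known only through intervention contacts.
- The TSC reviews both tables and keeps all decisions on pausing and stopping.
- Reconcile the Section 22 sentence that limits recording to related AEs and SAEs with the comparison of all SAEs in Sections 12 and 22.

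The cost is a little more form and table work, and care that the planned notes extraction is done the same way for all 84 participants. The common-source table is subject to nine-month attrition, and the fix removes bias without adding precision.
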